Oral PrEP is the latest biomedical intervention to be added to a growing of body of proven HIV prevention strategies. Oral PrEP is recommended by the World Health Organization and many Ministries of Health worldwide, including in Uganda, where HIV incidence is often greatest among young women [1-3]. In Uganda, clinical guidelines for PrEP became available in 2016 and the Ministry of Health is coordinating targeted scale up of PrEP for people with greatest HIV risk [2]. In Kampala, the capital city, PrEP is accessible through programs for key populations (e.g. sex workers, men who have sex with men, adolescent girls and young women (AGYW) and negative members of HIV serodiscordant couples, as well as through demonstration projects and clinical research.

As with any newly adopted intervention, there are key delivery questions that need to be understood to ensure efficient and effective scale up of PrEP on a population level. A large unanswered question for PrEP delivery is how well PrEP users execute daily pill taking and whether persistent PrEP use aligns with HIV exposure and risk. Initial demonstration projects among young women have found high degrees of PrEP uptake, with >80% of women offered in our ongoing program in western Kenya and South Africa [4]. However, programs are beginning to report high levels of client drop-off. Daily adherence is especially important for women to achieve tissue concentrations commensurate with HIV protection from PrEP [5]. Adherence may be greater among women who use PrEP for ≥ 3 months but it is not clear if adherence patterns and persistence align with HIV risk. Persistence with PrEP is important to provide protection during periods of oscillating HIV risk but PrEP could be discontinued when risk is no longer present (e.g. when a stable partner living with HIV is virally suppressed), thereby removing the low risk of medication toxicities [6].

PrEP adherence aligning with risk

A large unanswered question for PrEP delivery is how well PrEP users comply with daily pill taking and whether PrEP use aligns with HIV exposure and risk. Daily compliance with pill-taking is especially important for women to achieve tissue concentrations commensurate with protection

Table 1. **Scenarios of PrEP adherence and HIV risk in 7 days prior to sample/data collection.**

Green boxes indicate scenarios where PrEP use aligns with HIV risk.

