		Protection from PrEP (defined as TFV >40ng/ml or Wisepill data indicates 6-7 openings in the week prior to sampling)	Low/no protection from PrEP (defined as TFV <40ng/ml or Wisepill data indicates <6 openings in the week prior to sampling)
No sexual HIV risk: No sex in the past week	PrEP not necessarily needed if sex is not occurring and is not expected to occur soon	Lack of sufficient PrEP use aligns with lack of sex	
Low/No sexual HIV risk	PrEP aligns with HIV risk if condomless sex is anticipated in the near future	PrEP aligns with HIV risk if condomless sex is not anticipated in the coming week	
High sexual HIV risk	Possible sexual exposure to HIV aligns with PrEP adherence sufficient to provide protection from HIV infection	Possible sexual exposure to HIV and PrEP adherence insufficient to provide HIV protection	

TFV: tenofovir, the circulating metabolite of TDF-based medication that can be used as a marker of short-term adherence

from PrEP.[5] Initial demonstration projects of PrEP focusing on young women have found high degrees of uptake, estimated above 80% of women offered in our ongoing program in western Kenya and South Africa [4]. However, a number of programs are also beginning to report high levels of client drop-off. Adherence may be greater among women who use PrEP for ≥ 3 months but it is not clear if adherence patterns align with HIV risk. Continuous PrEP use is important to provide protection during periods of oscillating HIV risk but PrEP could be discontinued when risk is no longer present (e.g. when a partner living with HIV is virally suppressed, when a partnership is stably monogamous and both partners are HIV-negative), thereby removing side effects and the low risk of medication toxicities (Table 1 shows how PrEP use could overlay with HIV risk) [6].

Delivering PrEP to young women

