Kampala Women's Bone Study (KWBS)	
 • HIV • PrEP execution: 
 ◦ Tenofovir concentration in blood/urine ◦ Daily pillbox openings (Wisepill™) ◦ Self-report • PrEP persistence: 
 ◦ Pharmacy dispensation records • HIV risk 
 ◦ Yc DNA (marker of semen exposure/condomless sex) ◦ C. trachomatis ◦ N. gonorrhoeae
Young male partners of KWBS women joining the novel cohort established by the "Aligning PrEP and HIV exposure" protocol	
 • HIV • HIV risk 
 ◦ C. trachomatis ◦ N. gonorrhoeae • PrEP execution: 
 ◦ Tenofovir concentration in urine • Self-report

the men enrolling will be linked to data being collected among their young female sex partners in the Kampala Women's Bone Study, including women's adherence to PrEP, HIV status and STI diagnoses. The anonymous linkage of data between male and female sex partners will permit us to answer questions about HIV risk and exposure and how this aligns with PrEP use by each sexual partner.

Our parent study, the Kampala Women's Bone Study (KWBS)

We are currently conducting a longitudinal observational study of bone health among 500 women ages 16-25 who initiate PrEP concurrently with the common injectable contraceptive, depot medroxyprogesterone acetate (DMPA, R01HD089843 PI: [name]). In this study, we aim to determine whether young women using DMPA and PrEP will experience greater decreases in bone mineral density and markers of bone turnover and resorption relative to women using only one of the products (i.e. DMPA but not PrEP, PrEP but not DMPA) or neither. This clinically-driven parent study objectively measures bone health, PrEP adherence, and infection common curable STIs (Table 2). By anonymously linking data from the women in KWBS with data from their male partners, we can objectively measure alignment of PrEP use and HIV risk and exposure.

Recruitment for KWBS began in May 2018, 304 (60%) have been enrolled as of July 2019, and retention is high: only 5.2% of expected month-1, 2.2% of month-3, and 3.3% of month-6 visits have been missed to date. The cohort has self-reported high behavioral risk for HIV (**Table 3**), 22% were treated for a genital infection at enrollment (syndromically diagnosed), and 91% initiated PrEP at enrollment.

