protection (6-7 doses in the past week or TFV $\geq 40\text{ng/mL}$) for periods when women are dispensed PrEP. When PrEP is not dispensed, the TFV level will be assigned as 0 ng/mL .

For Aim 3, the primary outcome will be PrEP used by men with sufficient daily adherence to confer HIV protection (4 doses in the past week), measured by self-report or objective measures (daily monitoring or drug levels).

E. Hypothesis

Women and men will continue to use PrEP when their partners refuse HIV testing or disclose STI infections.

F. Location

This study will take place at the Infectious Diseases Institute (IDI)-Kasangati research clinic, located in the Kasangati area of Kampala in close proximity of several public health care facilities.

G. Population

The proposed study will enroll 200 young men who are male sexual partners of women in the current KWBS parent study. This demographic has a high risk for HIV acquisition thus it is ideal to provide them with diagnostic testing, prevention and treatment services for HIV and STIs, and prevent transmission to their female partners. Women from KWBS will also be engaged to discuss the study with their male partners and to have their data anonymously linked to their male partners who join this study.

H. Eligibility for men

Inclusion criteria:

- Men ages ≥ 18
- Has a female sexual partner enrolled in the Kampala Women's Bone Study
- Willing and able to provide informed consent

Exclusion criteria:

- Has any other condition that would preclude the ability to provide informed consent, make study participation unsafe, complicate the interpretation of study findings or otherwise interfere with achievement of the study objectives, in the investigator's discretion.

I. Eligibility for women

Inclusion criteria:

- Participating in the Kampala Women's Bone Study
- Willing to talk with male sex partners about the new study for men and refer men for study recruitment

Exclusion criteria:

- Has concerns about potential social harm stemming from anticipated conversations with male sex partners about the new study for men such that study staff would discourage the women from participation
- Investigator discretion

J. Sample size

We will enroll approximately 200 male and 300 female participants into this study

K. Study power

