Power calculations are based on the primary aim to determine alignment of women's PrEP use with male sex partner's STI infection status. Using an estimate that 20% of men will be infected with STI/HIV at any visit and 50% of their female partners will have protective PrEP levels, we estimate that we will have ≥80% power to detect a relative risk of ≥2.00 and ≥90% power to detect a relative risk of ≥2.30 in comparisons of the proportion of female visits with PrEP protection between visits when male partners had HIV risk or no HIV risk (assuming that $\alpha=0.05$). If 70% of their female partners have protective PrEP levels, power will be 80% for a RR of 1.57 and 90% for a RR of 1.72 (Table 4).

Table 4. Aim 2 power: Proportion of women with PrEP at protective level needed to see significant differences by male partner HIV risk, with ≥80% or ≥90% power.

Male partner HIV risk (HIV or STI infection)	PrEP at protective level, % (RR)	
Yes, exposed, N=40	50%	70%
Unexposed, N=160		
For 80% power	24.6% (RR=2.0)	44.6% (RR=1.5)
For 90% power	21.5% (RR=2.3)	40.8% (RR=1.7)

Power calculated by nQuery Advisor using power for Chisquared test comparing two

L. Recruitment

Overall

Women will be recruited to join this study by outreach staff at the IDI-Kasangati facility at the end of routine study visits for the KWBS.

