Men in this study will receive a study brochure from their female partner who is participating in the KWBS study. The brochure will have a label affixed to it with a code that is anonymously linked to the study ID of the woman recruiting him. At the time of presenting to the IDIK research clinic, potential male participants will be asked to bring their brochure so that the code can be scanned, and a male ID can also be linked to the same code. Using the code will enable women's ID to be linked to men's ID(s). If an enrolling participant does not have a coded brochure, we will create a link to a woman's ID by asking for the name of the woman who recruited him and accessing our link logs that are stored in a secure room with biometric access control.

VIII. DATA ANALYSIS

Data from each man and his female KWBS partner who recruits him will be longitudinally aligned using study visit dates. The primary exposure is male infection with HIV (Aim 1), NG, or CT (Aim 2), or female infection with HIV, NG, or CT (Aim 3) and the primary outcome will be PrEP used by women/men with sufficient daily adherence to confer HIV protection for periods when PrEP is dispensed. When PrEP is not dispensed, we will assign a TFV level of 0 ng/mL. We will estimate the association between HIV risk and use of PrEP using GEE to account for repeated measurements. Models will adjust for key confounding factors (demographic, sexual behavior, clinical).

IX. HUMAN SUBJECTS CONSIDERATIONS

The protocol, informed consent forms (for cohort participation and for interviews of providers), and patient education and recruitment materials will be reviewed and approved by the IRBs/ECs responsible for oversight. Subsequent to initial review and approval, the responsible IRBs/ECs will review the study at least annually.

A. Study oversight

The protocol study team will review a comprehensive set of safety and study operational data every 6 months to ensure that timelines are being met and the study will be able to answer its primary research questions.

B. Informed consent

We will perform paper-based consenting of participants in their preferred language. After we have ensured that participants have read and understood the consent forms, we will ask them to

append their signature on paper. Any participant who wants their consent form to take home will be given a copy.

C. Risks

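### Aim 2 aligns partners by visit date with no window or time order, so her one-week PrEP outcome can be paired with his NG/CT result from another week

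*Combined protocol and SAP*

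**What the plan says.** Section VIII (Data Analysis) gives the whole pairing rule in one sentence: "Data from each man and his female KWBS partner who recruits him will be longitudinally aligned using study visit dates". A GEE for repeated measurements follows. No section states how far apart the two partners' visits may be, which of her visits is used when several are candidates, or whether her PrEP week must come before or after his result.

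Her outcome is short-term. Section V.D defines protection as "6-7 doses in the past week" or TFV of at least 40 ng/mL. Table 1 is titled "Scenarios of PrEP adherence and HIV risk in 7 days prior to sample/data collection", and its protected column refers to "Wisepill data indicates 6-7 openings in the week prior to sampling". Section V.K describes the powered analysis as "comparisons of the proportion of female visits with PrEP protection between visits when male partners had HIV risk or no HIV risk".

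The two clocks are separate. Section V.N tests men for NG/CT at enrollment and 1, 3 and 6 months after their own enrollment, with immediate rapid results at enrollment and treatment provided for. Women attend KWBS visits. Their full schedule is not given, but the parent-study description reports that "only 5.2% of expected month-1, 2.2% of month-3, and 3.3% of month-6 visits have been missed to date". Under section V.L a woman is approached at the end of a routine KWBS visit and then speaks to her partner.

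Two other statements matter. The hypothesis in section V.E is "Women and men will continue to use PrEP when their partners refuse HIV testing or disclose STI infections". Table 2 lists "Daily pillbox openings" among the data already collected from the women.

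**The concern.** Table 1 frames adherence and risk over the same 7 days, but the analysis section does not require the two measurements to come from the same week. For Aim 2 two things follow.

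- **Dilution.** If her adherence varies from week to week, pairing his result with another of her weeks would usually pull the association toward the null.
- **Mixed questions.** Aim 2 asks whether her PrEP use matches his risk. The section V.E hypothesis asks what happens once he discloses. NG/CT is treated after a positive result, so a KWBS visit some weeks later may follow cure, disclosure, both or neither. Pooling her weeks before and after a result combines the two questions, and the effect could go either way. Her knowledge of his result cannot be assumed: assisted notification in section V.O is described for HIV, and section IX.C allows a man to keep his results confidential.

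Visit dates are recorded, so the gaps can be examined later. Without a rule fixed in advance, however, the pairing in the powered comparison would be chosen after the data are seen.

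**Working it through.** **1. The plan's own figure.** Table 4 (Aim 2) uses groups of 40 and 160 and alpha 0.05, taken here as two-sided. I used the continuity-corrected two-proportion formula with 160 at 50% and 40 at 24.6%:

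- The difference is 0.254 and the pooled proportion is (160×0.5 + 40×0.246)/200 = 0.449.
- The continuity correction reduces 160 to an equivalent 140.9, and √140.9 × 0.254 = 3.015.
- The null term is 1.96 × √(0.449×0.551×5) = 2.180. The alternative term is √(0.25 + 4×0.246×0.754) = 0.996.
- z = (3.015 − 2.180)/0.996 = 0.839, so power is 79.9%.

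The other three cells give 90.0%, 80.1% and 90.1%, so Table 4 reproduces. It treats every pair as correctly matched in time, with no allowance for mismatch.

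**2. How often the weeks match.** Assumptions, none of them in the documents: her visits are T days apart, his test falls at random between them, and the nearest visit is used.

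| Quantity | Formula | T = 91 | T = 30 |
|---|---|---|---|
| His test within 7 days of her visit | 14/T | 15% | 47% |
| Mean gap, days | T/4 | 22.8 | 7.5 |
| Her outcome week wholly after his result | ½(1 − 14/T) | 42% | 27% |

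**3. Favorable cases.** If he enrolls on the day of one of her visits and hers are 91 days apart, his tests at days 0, 30, 91 and 182 have gaps of 0, 30, 0 and 0 days, so 3 of 4 match. The only KWBS follow-up visits the protocol names are months 1, 3 and 6, the same as the men's. A man who enrolls within 7 days of his partner's own KWBS enrollment could match at 4 of 4. With 304 of 500 women enrolled by July 2019, 500 − 304 = 196 were still to come, so this is possible for some couples.

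**4. Which weeks precede a result.** Men are tested at enrollment and months 1, 3 and 6. The week before month 1, 3 or 6 follows at least one earlier result and possible treatment. Only the week before his first NG/CT test is free of any study result.

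**5. What a window costs in TFV.** Under the same model, her sample falls in the 7 days up to his test in 7/T of cases: 7/91 = 8% or 7/30 = 23%. Requiring her last visit to be within 14 days before his test keeps 14/91 = 15% or 14/30 = 47%. A 28-day limit keeps 28/91 = 31% or 28/30 = 93%.

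**The case against.** The strongest reply is that the text is underspecified but not shown to mismatch. Her openings are recorded daily, so aligning by visit date could already mean the week before his visit. That reading is open, but section V.K compares female visits and Table 1 ties the week to sampling, so it is not the natural one. One sentence in the plan would settle it.

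Second, the offsets may be far from random. Women are recruited at a KWBS visit, may bring partners to the clinic, and couples may attend together. This stands: the 15% and 47% are illustrations, and the match could be complete. These arrangements are optional, though, and nothing in the plan synchronizes the dates.

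Third, NG/CT reflects risk over more than one week, so a strict 7-day match may be too narrow. This also stands, and is why wider windows belong in a sensitivity analysis. It does not remove the before-and-after mixing.

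A reader might infer that Table 4's power falls by a definite amount. The documents do not support that. Any such figure needs the share of the association that survives in a mismatched week, and they give nothing on how stable her adherence is. I therefore quote no power loss. A reader might also extend the point to Aim 1. HIV status persists, so date gaps matter little there except around seroconversion.

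**Conclusion.** The point holds for Aim 2. The plan permits her one-week outcome to be paired with his NG/CT result from another week, and it does not separate her use before a result from her use after it. The gap in the text is certain; its effect is not. Matching within 7 days could be about 15% (91-day spacing) or 47% (30-day spacing) under random offsets with nearest-visit pairing, and up to 100% if the schedules coincide. There is no loss if her adherence is stable over the gap. Dilution is the likelier direction for mismatch unrelated to her PrEP use; mixing weeks before and after a result has no predictable direction. Daily openings are already collected for the women, so a better-timed outcome is available at low cost and should be specified before the data are analyzed.

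**What to change.** **Primary, Aim 2.** Define her outcome from daily Wisepill openings in the 7 days ending on each of his NG/CT test dates. Use TFV when her sample falls in that window. Keep the plan's either-measure definition and its rule for periods when PrEP is not dispensed. Otherwise set the pair-visit to missing.

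**Sensitivity.** Keep visit-date pairing, including TFV, using her nearest visit on or before his test with a stated maximum gap, for example 14 and 28 days. Report the distribution of gaps.

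**Time order.** Do not describe the primary analysis as pre-result. Report his first NG/CT test separately from later ones. The visit table marks STI testing at both screening and enrollment, so state which counts as first if these fall on different days. For each later outcome week, flag whether an earlier positive result preceded it. Treat her use in weeks after a positive result as a descriptive secondary analysis of the section V.E hypothesis, and acknowledge that these weeks overlap later primary weeks. The listed questionnaire topics do not name disclosure, so this analysis compares by his result unless an item is added.

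**Aim 1.** Leave the pairing unchanged and carry confirmed HIV-positive status forward. HIV testing stops after confirmation, so anchoring on HIV test dates would lose exposed pair-visits.

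**Minor safeguard.** Cluster the GEE on the woman's ID with robust variance. Section VII allows one woman to link to several men, and section VIII names no cluster unit.

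**Cost.** Analysis wording and programming, with no new visits or assays. The primary outcome would rest mostly on Wisepill, whose completeness the documents do not state, with TFV contributing in perhaps 8% to 23% of pairs under the random-offset model. Some pair-visits will be missing.

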Through our counseling, women are encouraged to use PrEP with high adherence and to discontinue PrEP during sustained periods with little risk. We are beginning to observe some PrEP discontinuations and some early decliners have initiated PrEP, indicating the potential for fluctuating risk and desire for PrEP.

Impact

By leveraging data already collected from young women in our ongoing study, the Kampala Women's Bone Study, and engaging a new cohort of young men for this protocol, we have an ideal platform to study whether PrEP use aligns with HIV exposure and sexual HIV risk among young women and their male sex partners, using objective measurement of HIV risk, PrEP adherence, and sexual behavior. An additional high impact result is an opportunity to identify strategies to engage young men in HIV prevention services through a novel cohort study. Findings demonstrating alignment of PrEP use and HIV risk will strengthen

Table 3. Characteristics of young women ages 16-25 enrolled in KWBS

Number enrolled (as of 15 April 2019)	240
Initiating PrEP at enrollment	91%
% expected M6 study visits not attended	3.3%
% accrued person time among women initiating PrEP at enrollment when PrEP was not dispensed (women switching on→off PrEP)	10%
% accrued person time among women non initiating PrEP at enrollment when PrEP was dispensed (women switching off→on PrEP)	17%
% aged 16-20	61%
Number of sex acts, past 3 months, median (IQR)	24 (9-72)
% sex acts, past 3 months, that were condomless	35%
Number of male sex partners, past 3 months, median (IQR)	2 (1-5)
% male partners that were new, past 3 months	40%
Treated for syndromically-diagnosed STI at enrollment visit*	22%

*Primary STI symptom was vaginitis or vaginal discharge.

confidence in programmatic PrEP delivery to young people. Findings demonstrating misalignment will be dissected to understand circumstances leading to over- or under-use of PrEP and opportunities for PrEP programs to improve alignment. All findings will be relevant for oral PrEP programs as well as novel PrEP strategies that are in the development pipeline, such as intravaginal rings and injectable PrEP.

V. METHODS

A. Overall Design

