The proposed research will engage a new cohort of young men, whose female partners are already engaged in the Kampala Women's Bone Study. Women in the Kampala Women's Bone Study will be invited to engage in this novel study to recruit their male partners. Women's HIV risk is directly related to the HIV status and risk of their male sexual partners and thus, we will leverage our ongoing cohort of KWBS young women to recruit their male sexual partners for a new men's study. Men will be offered PrEP, diagnostic STI testing and treatment, and followed for 6 months to assess PrEP continuation and STIs. Men's data will be linked to data from their female sex partners in the parallel KWBS study to determine whether women's PrEP use aligns with HIV risk and exposure.

B. Study Aims

Aim 1. To determine whether young women's adherence to PrEP aligns with the HIV status of their male partners

Men engaging in this study will have HIV testing at enrollment, month 1 and quarterly for up to 6 months. Results from this testing will be linked to data from the participant's female sex partner that characterize her PrEP use to determine whether her PrEP use aligns with his HIV status.

Aim 2. To determine whether young women's adherence to PrEP aligns with the HIV risk of their male partners

Men engaging in this study will have testing for common curable STIs (*Chlamydia trachomatis* and *Neisseria gonorrhoeae*) at enrollment, month 1 and quarterly for up to 6 months. Results from this testing will be linked to data from the participant's female sex partner that characterize her PrEP use to determine whether her PrEP use aligns with his HIV risk (defined by the results from his STI testing).

Aim 3. To determine whether young men's adherence to PrEP aligns with the HIV status and risk of their female partners

We will offer PrEP to HIV-negative men enrolled in this study and track PrEP initiation, refills, and adherence to PrEP (based on self-report and drug levels). The frequency of high PrEP adherence will be compared among men with female partners infected and uninfected with HIV or another STI.

C. Primary exposure

The primary exposure is male infection with HIV (Aim 1), NG or CT (Aim 2) and female infection with HIV, NG, or CT (Aim 3).

D. Primary outcomes

The primary outcome will be PrEP used by women with sufficient daily adherence to confer HIV Alignment PrEP and HIV Study Protocol

Version 1.0

23rd July 2019

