For young men who are sex partners of women in KWBS, we will leverage women participating in KWBS to recruit 200 of their current male sex partners. Women will be asked to consent to participate in recruitment of their male sex partners and to have their data anonymously linked to their male partner data. This will be a separate consent form and women may decline this component without any change to their participation in KWBS. Women with concerns about potentially experiencing violence from their male partner will be discouraged from recruiting this or any other male partners for the study and we will have staff trained in violence prevention available to counsel these women. The IDIK research clinic has established relationships with well-known organizations that specialize in IPV prevention and counseling in the event that a KWBS woman needs to be referred for more in-depth care. Ultimately, each woman's participation will be at her own discretion. Women engaging in this new study will be provided with multiple strategies to talk with male sex partners about the new study: talking points, recruitment brochures, HIV self-testing kits, and contact information for study recruitment staff.

Talking points

Women enrolled in KWBS will be provided talking points to guide them to think about how to recruit male partners. Talking points will include benign messages about a new research study for men and provide ideas about how to promote the men's study without disclosing information about their own recent HIV test/status or PrEP use (see Appendix for draft talking points).

Recruitment brochures

Women will also be given recruitment materials such as brochures, to give to their male partners that feature information on the benefits of STI testing and treatment, an introduction to PrEP and its availability for HIV-negative men through the study clinic. Recruitment materials will encourage men to call study recruitment officers or come to the IDIK research clinic. Draft brochures and other recruitment materials will be submitted to the research ethic committee for approval.

HIV self-test kits

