Following informed consent, men will be screened for their willingness to comply with study procedures, complete locator information, and assigned a unique ID. Eligible men will be enrolled into the study, on the same day if possible. Procedures on the day of enrollment will include: 1) HIV testing with PrEP dispensation or active referral to ART and HIV care depending on the results, 3) Hepatitis B and creatinine testing for men starting PrEP, 2) completion of questionnaires to assess demographic information, recent sexual behavior, partnership status, HIV risk perception, alcohol and drug use, mental health, and adherence to ART/PrEP, 4) diagnostic testing for *N. gonorrhoeae* and *C. trachomatis* using rapid tests with real time results. Results from creatinine testing will be available within 3-5 days from the laboratory. Any participants with abnormal creatinine/creatinine clearance will be contacted by the study clinician and asked to return for confirmatory testing. PrEP will be discontinued for any men with confirmed abnormal creatinine/creatinine clearance levels according to national guidelines.

Follow up

Follow up visits will be conducted 1, 3 and 6 months after enrollment. Procedures at each visit will include: 1) HIV testing with PrEP dispensation or referral to ART and HIV care depending on the results, 2) completion of questionnaires to assess recent sexual behavior, partnership status, HIV risk perception, and adherence to ART/PrEP, and 3) diagnostic testing and treatment for *N. gonorrhoeae* and *C. trachomatis*.

Aligning PrEP and HIV Study Protocol

Version 1.0

23rd July 2019

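### The analysis links each man to the woman who recruited him without requiring that they are still sexual partners, so visits after a partnership ends would count as partner exposure and dilute the alignment estimate

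*Combined protocol and SAP*

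**What the plan says.** **Entry.** Section V.H requires that a man "Has a female sexual partner enrolled in the Kampala Women's Bone Study". Section V.L plans to "recruit 200 of their current male sex partners". Both conditions apply at recruitment.

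**Linkage.** Section VII creates the link once, when the man presents, from a coded brochure or the link log: "Using the code will enable women's ID to be linked to men's ID(s)". No step updates or ends the link.

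**Follow-up.** Section V.N: "Follow up visits will be conducted 1, 3 and 6 months after enrollment". These visits include "completion of questionnaires to assess recent sexual behavior, partnership status, HIV risk perception, and adherence to ART/PrEP". The same section keeps men found HIV-positive in follow-up to the end of their time on study, without repeat HIV testing once the status is confirmed.

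**Exposure and alignment.** Section V.C: "The primary exposure is male infection with HIV (Aim 1), NG or CT (Aim 2)", and female infection for Aim 3. Section VIII: "Data from each man and his female KWBS partner who recruits him will be longitudinally aligned using study visit dates". The model is a GEE for repeated measurements, adjusted for demographic, sexual-behaviour and clinical confounders named only in general terms. Partnership status is not mentioned.

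**Context in Section IV.** Table 1 treats a week without sex as no sexual HIV risk. Women are counselled to stop PrEP in sustained periods of little risk. Under Section VIII, periods without dispensed PrEP are scored as a tenofovir level of zero.

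**The concern.** The aims ask whether PrEP use tracks the status and risk of a person's sexual partner. Once a couple has separated and no longer has sex, the former partner's later infection status is not an exposure. The exposure definition and the date-based alignment still treat it as one. Table 1 separates weeks with and without sex, but Section VIII does not carry that distinction into the exposure.

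Two things are at stake. First, if PrEP use after a break-up is unrelated to the former partner's status, those visits shrink the contrast between exposed and unexposed visits. Second, HIV status does not revert, so in Aim 1 an HIV-positive man remains the linked woman's exposure at every remaining visit. If she leaves him and stops PrEP because her risk is now low, she is coded as exposed and unprotected, although her behaviour fits the alignment that the study wants to measure.

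**Working it through.** **1. The plan's own figure.** Table 4 (Section V.K) has 40 exposed and 160 unexposed, with 50% against 24.6% protected for 80% power: RR = 50 / 24.6 = 2.03, printed as 2.0. A two-sided chi-squared test with continuity correction and the groups as labelled gives 82.4% power. With the lower proportion in the group of 40 it gives 79.9%, matching the table. For 70% against 44.6% the two figures are 78.5% and 80.1%. The orientation does not matter for this point; the groups are used as labelled below.

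**2. Share of visits after a break-up (assumption).** The documents give no break-up rate. Suppose 5–10% of partnerships have ended by month 1, 15–30% by month 3 and 30–50% by month 6. Planned couple-visits are 200 × 4 = 800 (enrolment and months 1, 3 and 6).
- Low: 10 + 30 + 60 = 100 visits, 100 / 800 = 12.5%.
- High: 20 + 60 + 100 = 180 visits, 180 / 800 = 22.5%.

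**3. Dilution over all visits.** Let f be the share of visits after a break-up, equal in both exposure groups, and q the proportion protected at those visits. Each group's proportion becomes p* = (1 − f)p + fq.

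*Model A: q = 24.6%, the unexposed level.*
- f = 0.125: 0.875 × 50 + 0.125 × 24.6 = 46.8%; RR = 46.8 / 24.6 = 1.90.
- f = 0.225: 0.775 × 50 + 0.225 × 24.6 = 44.3%; RR = 44.3 / 24.6 = 1.80.

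*Model B: q = overall average = 0.2 × 50 + 0.8 × 24.6 = 29.7%.*
- f = 0.125: 47.5% against 25.2%; RR 1.88.
- f = 0.225: 45.4% against 25.7%; RR 1.76.

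**4. Keep or exclude these visits (Model B).** Excluding them leaves 35 and 140 (f = 0.125) or 31 and 124 (f = 0.225), with the proportions unchanged.

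| Case | f | RR, kept | Power, kept | RR, excluded | Power, excluded |
|---|---|---|---|---|---|
| 50% vs 24.6% | 0.125 | 1.88 | 71% | 2.03 | 77% |
| 50% vs 24.6% | 0.225 | 1.76 | 61% | 2.03 | 71% |
| 70% vs 44.6% | 0.125 | 1.49 | 66% | 1.57 | 72% |
| 70% vs 44.6% | 0.225 | 1.43 | 54% | 1.57 | 65% |

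These powers use Table 4's 200 independent observations. They compare the two choices and do not forecast the power of the GEE.

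**5. Could the sign change?** With equal f and the same q in both groups, the difference is multiplied by (1 − f) and keeps its sign. With different shares f_e (exposed) and f_u (unexposed), the sign changes only if f_e > 1 − (1 − f_u)(p_u − q)/(p_e − q). Taking f_u = 0 and q = 0, the most favourable case for a reversal, the thresholds are 1 − 24.6/50 = 51% and 1 − 44.6/70 = 36% of exposed visits. With f_u = 20% and q = 0 they rise to 61% and 49%.

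**The case against.** **The plan is silent; it does not prescribe this.** No sentence says that visits after a break-up must be kept, and analysts might drop them. That is fair, and a reader should not infer a deliberate choice to keep them. But the written rule aligns on dates alone, the exposure has no partnership condition, and HIV-positive men are explicitly retained. Applied literally, these visits enter the model.

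**Adjustment for sexual behaviour may cover it.** A main-effect covariate does not correct an exposure that no longer applies. Partnership status is not named among the covariates.

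**Table 3 might be read as showing rapid break-up.** It gives a median of 2 partners (IQR 1–5) in 3 months and 40% for "male partners that were new, past 3 months". These figures describe all of a woman's partners, and their number and arrival. They are not the rate at which recruited partnerships end. Women choose whom to approach, so recruited couples may be more stable. The figures make some break-ups plausible and no more.

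**A former partner's result can still be informative.** Visits are one to three months apart, so an infection found soon after a break-up may date from the partnership. This stands, and the at-risk rule must keep such visits.

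**Stopping PrEP after leaving one man is not always alignment.** A woman with other partners may still be at risk. This also stands. The Aim 1 example holds only where her risk is in fact low.

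**Restriction can select.** A positive result, or its disclosure through partner notification (Section V.O), may itself end the partnership. Limiting the analysis to continuing couples then conditions on a possible consequence of exposure. This is a real cost and is the reason to report both analyses.

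**Conclusion.** The concern holds as a missing at-risk condition in the exposure definition. The expected direction is dilution. Assuming that 12.5% to 22.5% of couple-visits fall after a break-up, equally in both exposure groups, RR 2.03 becomes about 1.9 to 1.8 over all visits. Under the same assumptions, excluding those visits retains more power than keeping them. The true size is unknown because the documents give no break-up rate and no PrEP use after a break-up.

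Two stronger readings are not supported. One is that the result would be reversed. That needs many more break-ups among exposed couples and almost complete stopping of PrEP afterwards, and no figure in the documents points there. The other is to quote the month-6 effect alone: with 30% or 50% of partnerships ended, Model A gives RR 1.72 (42.4 / 24.6) or 1.52 (37.3 / 24.6). The GEE pools all visits, so these overstate the effect on the planned estimate.

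The Aim 1 miscoding of individual women does not depend on a reversal. It follows from a fixed link and an exposure that cannot revert.

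**What to change.** In Section VIII:
- Define exposure for the primary analysis of Aims 1–3 at visits with a reported ongoing partnership with the linked partner, or sex with that partner since the last visit. The second condition keeps infections found just after a break-up.
- Report the all-visits analysis as a sensitivity analysis.
- Report the number of couples ended by months 1, 3 and 6, by exposure status.

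In the questionnaire, make sure that the partnership item refers to the linked woman. Its wording is not in the documents, so it may already do so.

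The cost is a paragraph of analysis text and, at most, one reworded item, since partnership status is already collected. The downsides are fewer visits in the primary analysis, reliance on self-report, and possible selection if a positive result or its disclosure ends partnerships. The all-visits analysis and the counts by exposure status would show whether such selection matters. The rule should be set before linked data are examined.
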